6. DATA ANALYSIS

6.1. Data Quality Assurance

All the data will be obtained from the tumour board list. The investigator will ensure the data entries are accurate and correct.

6.2. Data Entry and Storage

All the data will be handled confidentially and anonymously.

In part 1 and 2, the data will be entered into a password encrypted excel sheet and de-identified by a central third party. The individual-identifiers will be kept by the central third party.

In part 3, the anonymous data will be fed into the AIM online platform directly. Only registered user can feed the data into the AIM online platform. A subject identification code will be assigned to each patient and the subject code list is kept within the institution. Ping An team will be responsible for extracting the data for concordance analysis.

7. STATISTICAL ANALYSIS

Descriptive statistics for both the patient population as well as cancer characteristics would be calculated and tabulated in means and medians where appropriate.

Concordance would be calculated and presented as percentages.

8. ETHICAL CONSIDERATIONS

8.1. Regulation statement

The study will be conducted in accordance with the protocol, International Conference on Harmonization (ICH) GCP guidelines, applicable regulations and guidelines governing clinical study conduct and ethical principles that have their origin in the Declaration of Helsinki. The investigator must ensure that the study is conducted in accordance with the provisions as stated in the ICH regulations and complies with prevailing local laws and customs.

8.2. Informed Consent

These procedures may differ per country. In general, prior collecting patient data, the investigator or his/her representative will explain the nature of the study to the subject and answer all questions regarding this study. Each informed consent will be reviewed, signed and dated by the subject and the person who administered the informed consent. A copy of each informed consent will be given to the subject and each original will be placed in the subject's medical record.

8.3. IRB review

Each participating institution must provide for the review and approval of this protocol and the

associated informed consent documents by the local IRB prior conducting any research activities.

Any amendments to the protocol will require local IRB approval prior to implementation of any changes made to the study design. All substantial amendments will be notified to the IRB and to the competent authority. Non-substantial amendments such as administrative changes will not be notified to the local IRB and the competent authority, but will be recorded and filed by the sponsor.

The sponsor/ investigator will submit a summary of the progress of the trial to the local IRB yearly.

The end of the study is defined as 100 valid cases has been recorded per institute. In case the study is ended prematurely, the investigator will notify the local IRB within 7 days, including the reasons for premature termination. Within 30 days after the end of the study, the investigator/ sponsor will submit a final study report with the results of the study, to the local IRB.

8.4. Confidentiality of Data and Patient Records

Information collected for this study will be kept confidential. This confidentiality is extended to cover testing of biological samples and genetic tests in addition to the clinical information relating to the participating subjects. Patient records, to the extent of the applicable laws and regulations, will not be made publicly available. Data collected and entered into the AIM online platform are the property of NUH and Ping An. In the event of any publication regarding this study, patient's identity will remain confidential.

9. RETENTION OF TRIAL DOCUMENTS

Records for all participants, including CRFs, all source documentation (containing evidence to study eligibility, history and physical findings, laboratory data, results of consultations, etc.) as well as IRB records and other regulatory documentation should be retained by the PI in a secure storage facility for up to 6 years. The records should be accessible for inspection and copying by authorized authorities.

10. AUTHORSHIP

10.1. Writing committee on behalf of the study group

Centers providing at least 50 cases will be eligible for 1 authorship position within the writing committee, with eligibility for 2 authorship positions when providing at least 100 cases. Each participating center will decide internally which local investigator will be the principal investigator (PI) and who will be listed as a co-author/s within the writing committee should the center fulfil the criteria mentioned. The study coordinator ([name]) will be the first author. The corresponding authorship position is reserved for the project leader ([name]). The last author position is reserved for the project co-leader ([name]). The remaining co-authors within this study group will be listed according to the number of patients recruited per center. The center with the highest recruitment numbers will take the second and third authorship positions. Any publication, presentation or abstract on collected data will be delegated to all authors. Each center keeps ownership of their own data and additional reports on data collected will only be conducted with written permission from each center's PI. All participating authors can suggest alterations to the study design or additional analyses. All the principal investigators together with the study coordinators and project leader constitute the steering committee of the project. These rules are subject to the verification that data collected from the recruited patients are complete and to the satisfaction of the study project leader and co-leader, with ranking priority given to centers with complete datasets.

10.2. Study group authorship

This group of co-authors will be collectively listed under the study group name (AI Multidisciplinary Tumour Study Group – AIM Study Group). This list of co-authors will be submitted, indexed and linked to any publication associated with this study group where possible. Centers who recruit at least 25 patients for this study will be eligible to include 2 co-authorship positions in this list. This will be in addition to the authorship positions given for centers that recruit at least 50 or 100 patients.

10.3. Acknowledgments

All centers that participate in this study are eligible to provide 2 names for acknowledgement in this study. This is in addition to the authorship positions given in the writing committee and study group for eligible centers.

Appendix 1: Example of AIM Platform

 **Clinical Information**

Label

* Age * Gender * Diagnosis

General Information

* Type of Case? New Case Case after Primary Treatment Recurrence

* Primary Treatment?

Endoscopic resection Surgery Neoadjuvant Chemotherapy or Chemoradiation

Chemoradiation, Systemic therapy or Best supportive care

* Tumor classification? (M) M0 M1

* Tumor classification? (T)

Tis T1a T1b T2 T3 T4 T4a T4b

* Tumor classification? (N) N0 N1 N2 N3 N3a N3b

Further Information

Type of Resection? R0 R1 R2

* Have Received Neoadjuvant Chemotherapy or Chemoradiation?

Neoadjuvant Chemotherapy Neoadjuvant Chemoradiation None

Type of lymph node dissection? D1 D2

Figure 1. AIM Online Platform for Gastric Carcinoma

Clinical Information

Label

* Age * Gender * Diagnosis

General Information

* Histologic Classification? Squamous cell carcinoma Adenocarcinoma

Type of GEJ? Stewart Type 1 Stewart Type 2 Stewart Type 3 Unspecified

* Type of Case? New Case Case after Primary Treatment Recurrence

* Tumor classification? (M) M0 M1

* Tumor classification? (T)

Tis T1a T1b T2 T3 T4 T4a T4b

* Tumor classification? (N) N0 N1 N2 N3 N3a N3b

Further Information

ECOG? 0-2 ≥3

Serum creatinine? Normal Abnormally High

Medically fit for surgery? Yes No

Surgically resectable? Yes No

Bulky N? Yes No

The presence of complications? (Bleeding, obstruction, or perforation) Yes No

Figure 2. AIM Online Platform for GEJ Carcinoma

Treatment Recommendation(s) Switch to browse by guideline ⇌

1st Recommendation
2nd Recommendation
3rd Recommendation

- Surgery (may followed by adjuvant therapy)**
 Supported by JGCA 2018
- Chemoradiation**
 Supported by NCCN 2020
- Systemic therapy**
 Supported by NCCN 2020
- Neoadjuvant chemotherapy**
 Supported by ESMO 2016

Your Treatment Option

Please enter your treatment option

Comment

Please enter your comments

Save

Figure 3. Example of AIM Treatment Recommendations

Clinical Information:  Male | 85 | Gastric cancer | T3N3M0 |

Recommended by Guidelines:

-  **Surgery**
(may followed by adjuvant therapy)
-  **Chemoradiation**
-  **Systemic therapy**
-  **Neoadjuvant chemotherapy**

Other Recommendations 

-  **Chemotherapy**
-  **Radiation**
-  **Neoadjuvant chemoradiation**
-  **Best supportive care**

Guideline(1) Meta-analysis(26) RCT(49)

1. **Japanese: Gastric Cancer Guidelines for treatment (Version 5.2018)**

Recommendation: Standard gastrectomy, D2 (may followed by adjuvant therapy)

Citation: A D2 lymphadenectomy is indicated for potentially curable cT2–T4 tumors as well as cT1N+ tumors. Spleen should be preserved in total gastrectomy for advanced cancer of the upper stomach provided the tumor does not involve the greater curvature. The role of splenectomy for tumors invading the greater curvature remains equivocal.

Reference

[Randomized Controlled Trial to Evaluate Splenectomy in Total Gastrectomy for Proximal Gastric Carcinoma.](#)

2017,02 | Randomized Controlled Trial | Annals of surgery **IF:9.48**

Figure 4. Example of AIM Reference Page

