2.2. Primary Objectives

Comparative agreement in recommendations between the two study groups, as measured by concordance rate.

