2.3. Secondary Objectives

To identify the reason for the discordance.

2.4. Potential Risks and benefits:

There is minimal risk to our patients as the treatment is still decided by the clinical team as per clinical practice. The comparison is made by our research staffs. The recommendation by Artificial Intelligence Multidisciplinary Tumour Board online platform (AIM online platform) is made available to the clinicians. The clinicians can refer it as an option for their consideration. The risk of the study is related to the data breach during data collection. However, this risk will be minimised by de-identifying using a unique code number and only the study team member will have access to the patient identification.

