5. STUDY DESIGN

Our study comprises three parts: The Discovery Part (Part 1), The Internal Retrospective Validation Part (Part 2) and The Prospective Validation Part (Part 3).

In the discovery part, de-identified retrospective data on patient and disease characteristics as well as our MDTM recommendations would be collected and utilized to develop the CDSS platform, named AIM online platform, with help from our collaborative partner, Ping An Technology (Shenzhen, China).

In the internal retrospective validation part, additional de-identified retrospective data different from the discovery part will be entered manually into AIM online platform by two trained clinicians, who would be blinded to the treatment recommendations given by the MDTM. These treatment recommendations for each patient would then be collated and compared to the MDTM recommendation. Concordance would be determined by whether the MDTM recommendation is listed in AIM's list of treatment recommendations as a) 1st Recommendation, b) 2nd Recommendation, c) 3rd Recommendation, or d) Not Concordance.

In the external validation part, prospective patient data would be collected over a period of 2 to 3 years from more than 10 different institutions, including centres from Europe, North America and Asia. The prospective data is defined as data collected after 1 May 2020, and the study team will only be collecting data from participants who have given their consent (this may differ per country as per local IRB's requirement). These patient data would be fed into the AIM online

platform within one month of MDTM discussion at these institutions, with clinicians blinded to the generated recommendations. These recommendations would then be immediately compared to the MDTM recommendations to determine concordance. Concordance would be determined by whether the MDTM recommendation is listed in AIM’s list of treatment recommendations as a) 1st Recommendation, b) 2nd Recommendation, c) 3rd Recommendation, or d) Not Concordance. All these data will be captured in the AIM platform.

[figure not shown]

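### Concordance is scored by whether the board's plan is listed by AIM, but the example screen takes that plan beneath AIM's displayed list and the labels partly overlap, so the match, and especially its rank, can depend on the reader

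*Protocol*

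**What the plan says.** Section 2.2 gives the primary objective: "Comparative agreement in recommendations between the two study groups, as measured by concordance rate". Section 5 (Study Design) defines the measure, in the same terms for the retrospective and the prospective validation: "Concordance would be determined by whether the MDTM recommendation is listed in AIM's list of treatment recommendations as a) 1st Recommendation, b) 2nd Recommendation", then third recommendation, or not concordant. It does not say at what level of detail a plan counts as listed (modality, sequence, adjuvant component).

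Section 2.4 says who compares: "The comparison is made by our research staffs". Section 6.2 adds: "Ping An team will be responsible for extracting the data for concordance analysis".

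Appendix 1 shows example screens. Figures 1 and 2 are the case input forms, and neither shows a field for the board's plan. Figure 3 shows AIM's ranked options and, after them, the prompt "Please enter your treatment option", followed by a comment box prompted by "Please enter your comments". Figure 4 repeats the four options of Figure 3 as guideline-recommended and adds four more in a separate block of other recommendations.

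On blinding in the prospective part, Section 5 says that clinicians are blinded to AIM's recommendations. Section 2.4 says that the recommendations are made available to clinicians, who may consider them.

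**The concern.** A concordance rate is only as objective as the rule that turns two recommendations into match or no match. Here the rule is that one is listed in the other. That is clear only if both sides use the same categories and the board's side is fixed before the other is seen. The example screens suggest that neither holds. The option labels overlap, and the entry field stands on the screen that already displays AIM's answer.

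A person who codes a compound plan with the list in view will tend to choose the wording that fits. This needs no bad faith, and it pushes in one direction, towards agreement and towards the higher rank. More patients do not reduce it. It could differ between sites and over time. Section 5 plans site-specific rates and a rate in each of two stages, with the model retrained in between, so a difference in coding habit could not be told apart from a difference in the algorithm's performance.

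**Working it through.** **1. Order of entry.** Under Section 5, case data go into AIM within one month of the board's discussion, so the board's decision already exists and AIM cannot change it. What remains open is how that decision is coded. Section 5 says that all these data are captured in the platform, and the only field for a treatment option in the example screens is the one in Figure 3, after AIM's list. That the board's plan is entered there is an inference, but it is the only route shown. In the retrospective validation, those who enter the cases are blinded to the board's recommendation, which protects the input to AIM. In neither part is the person who judges the match said to be blinded to AIM's list.

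**2. The labels, tried on three plans.**

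| Board's plan | Possible readings | What can change |
|---|---|---|
| Chemotherapy as the main treatment | *Systemic therapy* (Figures 3 and 4) or *Chemotherapy* (Figure 4, other recommendations only) | Match or no match, because the protocol does not say whether the second block counts as listed |
| Chemotherapy, then surgery | *Neoadjuvant chemotherapy* or *Surgery* | The rank; both are listed in Figure 3, so the any-rank result there is concordant either way |
| Surgery alone, or surgery plus adjuvant treatment | *Surgery*, with the rider "may followed by adjuvant therapy" | Nothing: where surgery is listed, both plans match and the rate cannot tell them apart |

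The first two rows leave a choice to the reader. The third is a limit of resolution and involves no judgement.

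**3. Blinding.** If the clinicians of Section 5 include whoever completes Figure 3, the screen as shown is at odds with the blinding statement. Sections 5 and 2.4 also differ on their face about whether clinicians see AIM's output.

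**4. How much re-reading would matter.** The protocol gives no expected concordance or precision target, so there is no planned figure to reproduce. Its case numbers agree: 500 + 1000 = 1500 (Sections 5 and 3.1). As a yardstick, the 95% half-width of a proportion p is 1.96 × √(p(1 − p)/n). The values of p are assumptions.

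- n = 1500: p = 0.5 gives 2.53 points; p = 0.7 gives 2.32; p = 0.9 gives 1.52. Multiplied by 1500, that is about 38, 35 and 23 cases.
- n = 500 (Stage 1): 4.38, 4.02 and 2.63 points, or about 22, 20 and 13 cases.

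A net change in reading of that many cases would move the rate by as much as its sampling half-width. The same holds for the share matched at first rank, with p read as that share. This shows how few cases would matter. It does not show how many are affected.

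**The case against.** The strongest reply is that Section 5 does define the endpoint, with four ordered categories, and that a mapping table or coding manual may exist elsewhere. The screens are captioned as examples. The input forms record the treatment point (new case, after primary treatment, recurrence) and list neoadjuvant treatment apart from surgery, which suggests that the labels describe the next or main step. On that view chemotherapy before surgery has a natural label. *Chemotherapy* appears only on the reference page, for one case without distant metastasis, and not on the screen with the ranks.

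Much of this stands and limits the point. It does not answer the order of entry. A manual written later cannot undo coding done with AIM's list in view, or recover sequence detail that was never captured.

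A reader might infer more than the documents support:

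- **That the plan is free text.** The prompt resembles that of the comment box, but a pick list is possible. Overlapping labels leave a choice either way.
- **That a surgical plan can never be discordant.** It is discordant whenever AIM does not list surgery. Only the adjuvant component cannot disagree.
- **That the developer steers the result.** Section 6.2 has its team extract data. Nothing says that it judges matches or selects cases.
- **That the rate is inflated by some stated number of points.** Any assumed share of ambiguous cases simply returns itself as the shift, and some of those cases would change only rank.
- **That an improvement from Stage 1 to Stage 2 would be spurious.** Section 5 analyses concordance in each stage and states no formal comparison between them.

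**Conclusion.** The point holds in a limited form. As the protocol and its example screens stand, the primary endpoint rests on a judgement that can be made with AIM's answer in view, against labels that are not mutually exclusive. Rank is the most exposed. Whether a case counts as concordant at all is exposed mainly where a plan fits a label in the second block of Figure 4. The expected direction is upward. The size is unknown, because the documents do not show how many plans fit two labels or how staff would code them.

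The conclusion assumes that the working platform follows the example screens and that the Figure 3 field is where the board's recommendation is recorded. If the plan is in fact locked before AIM's output appears, the main bias route is closed and only the question of label and rank remains. The conflict between Sections 5 and 2.4 on what clinicians see stands in either case and must be reconciled. The point is worth settling before Stage 1 because the remedy is cheap and the capture cannot be repaired afterwards.

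**What to change.** - Record the board's recommendation on the case input form, from a closed list that includes an entry for other plans with details, and lock it before AIM's output is displayed.
- Before Stage 1, fix one mapping from these categories to AIM's existing labels. State which rank counts when a plan fits two labels, and whether the other recommendations of Figure 4 count as listed.
- Have the platform compute concordance from that mapping. Map the other-plan entries without sight of AIM's list.
- Leave AIM's output labels unchanged; rewriting them would alter the system under validation.
- Take a complete locked export for the analysis.
- Reconcile Sections 5 and 2.4 on whether clinicians see AIM's recommendations.

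The cost is a small form change, a mapping to agree and a few lines of protocol text, with no extra patients or staff. The downside is a rate that may be somewhat lower than under lenient reading. The mapping will not separate surgery alone from surgery plus adjuvant treatment, since AIM's label does not, so the report should say that concordance is silent on that component.

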Appendix 3: ICMJE Criteria For Joined Authorship

Source: http://www.icmje.org/ethical_1author.html

The ICJME has recommended the following criteria for authorship; these criteria are still appropriate for journals that distinguish authors from other contributors.

- Authorship credit should be based on 1) substantial contributions to conception and design, acquisition of data, or analysis and interpretation of data; 2) drafting the article or revising it critically for important intellectual content; and 3) final approval of the version to be published. Authors should meet conditions 1, 2, and 3.
- When a large, multicenter group has conducted the work, the group should identify the individuals who accept direct responsibility for the manuscript (3). These individuals should fully meet the criteria for authorship/contributorship defined above, and editors will ask these individuals to complete journal-specific author and conflict-of-interest disclosure forms. When submitting a manuscript authored by a group, the corresponding author should clearly indicate the preferred citation and identify all individual authors as well as the group name. Journals generally list other members of the group in the Acknowledgments. The NLM indexes the group name and the names of individuals the group has identified as being directly responsible for the manuscript; it also lists the names of collaborators if they are listed in Acknowledgments.
- Acquisition of funding, collection of data, or general supervision of the research group alone does not constitute authorship.
- All persons designated as authors should qualify for authorship, and all those who qualify should be listed. Each author should have participated sufficiently in the work to take public responsibility for appropriate portions of the content
